2.1.1 General definitions

‘**Actual dose**’ will be derived as the current dose for each subject on a daily basis across the entire study; in the case of the day of a dose change, the new dose will be used.

‘**Treatment group**’ in Parts 2 & 3 will refer to the treatment group combination (as mentioned above) for efficacy analyses, and to the actual treatment for safety analyses (see definition below). In Parts 1 & 3, this will be Overall.

‘**Cohort**’ will refer to the initial dose for baseline or demographic characteristics.

The term ‘**Study Day**’ in this document relates to the Analysis Relative Day, Relative Start Day or Relative End Day as applicable. ‘**Study Day**’ is defined relative to the analysis reference date, which is the date of treatment assignment; it is the number of days from the reference date to the analysis date. For all dates on or after the analysis reference date, the study day is the difference to the analysis reference date plus one day (i.e. for date \geq reference date, study day = date - reference date + 1); for any dates prior to the analysis reference date, the study day is

simply the difference to the reference date (i.e. for date < reference date, study day = date - reference date). Thus, the Subject Reference Start Date is designated as Study Day 1, while the date directly prior to the reference date is defined as Study Day -1 (there is no Study Day 0).

'Baseline' is the last non-missing assessment obtained prior to the first administration of study drug. That means that if the measurement at the baseline visit is missing, then the previous measurement preceding baseline will be used as the baseline measurement. For pulse and blood pressure vital sign values, the baseline is the last non-missing value taken prior to the first administration of study drug.

'Treatment phase' includes the time interval on treatment and post-treatment follow-up. Any measurements taken after baseline will be considered as post-baseline measurements.

'Actual treatment' is defined as the treatment group the patient has most exposure to in each Part (for Parts 2 & 3), leading to a treatment group combination; in the case of two treatments having identical exposure, the higher dose will be used. This will be used for safety analyses.

'Calendar age' is defined as the age at the date of evaluation.

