2.2 Analysis sets

The following populations will be used for the statistical analyses:

Enrolled Set (ENR) will consist of all subjects giving study informed consent and are assigned a treatment.

Full Analysis Set (FAS) will consist of all subjects in the Enrolled Set who received at least one dose of study drug. Patients will be analyzed according to the treatment group (as defined in [Section 2.1.1](#)).

Safety Set (SAF) will consist of all subjects in the Enrolled Set who received at least one dose of study drug. Patients will be analyzed according to the actual treatment received (as defined in [Section 2.1.1](#)). The Safety Set will be used for the analyses of safety variables.

Dose Determining Set (DDS) (Part 1 only) will consist of all subjects from the safety set who have sufficient safety evaluations to provide DLT information 2 weeks after the first dosing or discontinue earlier due to DLT. Subjects who do not experience DLT during the first 2 weeks after the first dose are considered to have sufficient safety evaluations if they are considered by both the Sponsor and Investigators to have sufficient safety data to conclude that a DLT did not occur.

PK Analysis Set will include all subjects that received at least one dose of branaplam with available PK data and no protocol deviations with relevant impact on PK data. The PK Analysis Set will be used for the analyses of PK variables.

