2.8 Safety Analyses

In general, data assigned to Part 3 (section 2.1.1) will be analysed together with the part the subject came from (i.e. 'Parts 1 & 3', 'Parts 2 & 3').

Safety analyses will be conducted using the safety set (SAF). In Parts 1 & 3, subjects will be analyzed overall, with some graphical methods including the current dose; in Parts 2 & 3, the analyses will be summarized by actual treatment group. Unless explicitly stated otherwise, only data up to the safety cutoff (as defined in [Section 2.1.1](#)) will be included in the analysis and data beyond this time point for a given subject will be excluded from the safety analysis.

The assessment of safety will be primarily based on the frequency of adverse events (including death and non-fatal serious adverse events), and adverse events of special interest. Additional safety assessments include laboratory tests, ECG evaluations, echocardiograms, vital signs, ophthalmology, physical and neurophysiological examinations. Clinically significant findings

in these additional safety assessments will be reported as adverse events and analyzed as such. In addition, all safety assessments will be summarized or listed as appropriate.

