2.8.2 Adverse events (AEs)

An adverse event (AE) is any untoward medical occurrence (i.e., any unfavorable and unintended sign [including abnormal laboratory findings], symptom or disease) in a subject or clinical investigation of a subject after providing written informed consent for participation in the study. That means that a subject can report AEs before having started study drug. For reporting purposes, the main focus will be on treatment emergent adverse events (TEAEs). Treatment emergent AEs are defined as events starting on or after the first dose of study drug that were absent pre-treatment, or events present prior to the first dose but increased in severity after the first dose (based on the MedDRA lower level term (LLT)). TEAEs are included up to the safety cutoff (as defined in [Section 2.1.1](#)). Except for serious TEAEs and death, only TEAEs up to and including safety cutoff (as defined in [Section 2.1.1](#)) will be included in the analyses. For serious TEAEs a modified safety cutoff is used (as defined in [Section 2.1.1](#)). TEAEs will be assigned to Part 3 if the start date is on/after the first visit date of Part 3 (see section 2.1.1). All deaths will be included, regardless of safety cutoff.

AEs will be reported by primary system organ class (SOC) and preferred term (PT) according to the Medical Dictionary for Regulatory Activities (MedDRA). The MedDRA version used for reporting the study will be described in a footnote.

The number and percentage of subjects reporting any TEAEs will be summarized by primary SOC, preferred term, maximum CTCAE grade (individual, as well as Grade 3 and above combined) and treatment group (Parts 2 & 3). Missing CTCAE grade will not be imputed. Separate summaries will be provided for serious TEAEs, drug related TEAEs, TEAEs leading to permanent discontinuation of study drug and most common TEAEs (10% in any group). Furthermore, exposure-adjusted incidences will be reported in an AE overview table, for all AEs in a table by system organ class and preferred term by part, and similarly for serious AEs.

If a subject reported more than one adverse event within the same primary system organ class, the subject will be counted only once with the maximum CTCAE grade at the system organ class level, where applicable.

All AEs will be presented in listings.

The following graphs will be displayed:

- Bar charts of MedDRA system organ classes - crude incidences

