2.8.2.1 Adverse events of special interest / grouping of AEs

Selected tables will be produced for Adverse Events of Special Interest (AESI) (i.e., risks) defined in the latest version of case retrieval sheet (eCRS) at the time of analysis implementation (i.e., study database lock).

The LMI070X2201 eCRS is available at <http://go/ecrs> by selecting either

- CRS NAME: (LMI070 Spinal muscular atrophy) or
- CRS ID: 3689
- Within the document, select SP="Y"

Specifically, incidence of TEAEs that fulfill the risk search terms as defined in eCRS will be summarized by risk name, level, study part and treatment group (for Parts 2 & 3 only) with crude incidences and 95% confidence intervals presented.

Similarly, separate summaries will be provided for serious TEAEs that fulfill the risk search terms as defined in eCRS. Additionally, incidence of any TEAEs that fulfill the search terms as defined in eCRS will also be summarized by risk name, level, and maximum CTCAE grade.

Bar charts of MedDRA preferred terms that fulfill the search terms as defined in eCRS will be produced for crude incidences by part.

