2.8.4 Laboratory data

Data summaries will be provided in SI units. The summary of laboratory evaluations will be presented for three groups of laboratory tests: Hematology, Chemistry and Urinalysis. On presenting summary statistics, laboratory data will be grouped and displayed in an alphabetical order within each of the three groups.

Descriptive summary statistics (mean, median, standard deviation, Min and Max) of the change from baseline in the laboratory result to each study visit-window by treatment group will be presented for continuous variables. Change from baseline will only be summarized for subjects with both baseline and post baseline values and will be calculated as:

$$\text{change from baseline} = \text{post baseline value} - \text{baseline value}$$

In addition, shift tables will be provided for all parameters to compare a subject's baseline laboratory evaluation relative to the post-baseline values. For the shift tables, the normal local

laboratory ranges will be used to evaluate whether a particular laboratory test value was normal, low, or high relative to whether or not the baseline value was normal, low, or high. These summaries will be presented by laboratory test overall in Parts 1 & 3, additionally by actual treatment group in Parts 2 & 3. Shift table will also be provided for urinalysis results to compare baseline to post-baseline extreme values (negative, +, 2+, 3+, or 4+).

Number of subjects with newly occurring liver enzymes abnormalities will be summarized using the respective criteria. Newly occurring liver enzymes abnormalities are defined in [Section 5.3.2](#).

For both shift tables and newly occurring liver enzymes abnormalities, all applicable post-baseline values (including unscheduled or unplanned visits) will be checked against the respective criteria and the rules for handling multiple laboratory assessments within visit windows will not be applied.

For continuous variables databased as <lower limit, these will be imputed as being half of the lower limit.

The following graphs will be generated for liver enzymes:

- Panel plot of individual subjects for alkaline phosphatase, total bilirubin, ALT and AST with dose as background shading – one panel per subject (Parts 1 & 3 and Parts 2 & 3)
- eDISH scatterplot of Total Bilirubin and ALT on log-log axes (Parts 1 & 3); additionally stratified by treatment group (Parts 2 & 3)

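### Parts 2 & 3 safety tables label each child by the majority dose in each Part, so events on the minority dose are shown under the other dose or in a mixed column, and no incidence table by dose at onset is planned

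*SAP*

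**What the plan says.** SAP 2.1.1 sets the safety grouping for Parts 2 & 3. *Actual treatment* is "the treatment group the patient has most exposure to in each Part (for Parts 2 & 3), leading to a treatment group combination", and "in the case of two treatments having identical exposure, the higher dose will be used". SAP 2.2 applies this to the Safety Set ("Patients will be analyzed according to the actual treatment received"), and SAP 2.8 does the same ("in Parts 2 & 3, the analyses will be summarized by actual treatment group").

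The outputs that use the grouping are:

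- TEAE tables, by "maximum CTCAE grade (individual, as well as Grade 3 and above combined) and treatment group (Parts 2 & 3" (SAP 2.8.2)
- special-interest AE incidences, by "study part and treatment group (for Parts 2 & 3 only) with crude incidences and 95% confidence intervals presented" (SAP 2.8.2.1)
- laboratory shift tables, overall in Parts 1 & 3 and "additionally by actual treatment group in Parts 2 & 3" (SAP 2.8.4)
- patient-years by treatment group (SAP 2.4.1)

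SAP 2.1.1 also defines a separate daily variable, *Actual dose*, which "will be derived as the current dose for each subject on a daily basis across the entire study". The SAP uses current dose for graphics, such as background shading, and assigns no AE incidence table to it.

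Two other places group differently. Protocol 11.1 takes the dose of the initial treatment period as the general rule and lets actual dose be used in some inferential analyses. SAP 2.1 uses the fixed Part 2 dose as the stratum and gives upward moves in Part 3 no analysis of their own. SAP 2.5 states that AE information will be shown by starting dose, administered dose and child.

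**The concern.** One label per Part can describe a dose change that falls exactly at Part 3 entry, because the two labels are joined. It cannot describe a change inside a Part. Two situations follow.

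1. **The two labels match.** A child escalated early in Part 2 is labelled 2.5/2.5, and the 0.625 mg/kg events and time count under 2.5. A child moved to 2.5 mg/kg late in Part 3 is labelled 0.625/0.625, and the events after the move count under 0.625.
2. **The two labels differ.** A child escalated late in Part 2 who stays on 2.5 mg/kg is labelled 0.625/2.5. Events at either dose fall in a mixed column that attributes them to neither.

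Safety and tolerability of the two doses is the Part 2 primary objective (SAP 1.1.1). The group tables alone would not show which events began on the other dose; a reader would have to rebuild this child by child.

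**Working it through.** **Do dose changes inside a Part arise?**

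- *Part 2.* SAP section 1 allows escalation from 0.625 to 2.5 mg/kg as an exception. Its Part 3 dose rationale mentions lower-dose children who did better after going up and tags this as Part 2. The tag could mean children from Part 2 rather than switches during it.
- *Part 3.* Protocol 3.3 allows changes in both directions. Protocol 3.5.3 and 5.4.3 say sites were asked to move all children to 2.5 mg/kg, with exceptions, after the Part 2 analysis. Protocol 11.4 places that analysis after every Part 2 child had completed 52 weeks, and SAP section 1 says the cohorts opened in sequence. A child already in Part 3 on 0.625 mg/kg at that point changes dose inside Part 3, not at entry.

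**Which outputs are affected?** Those listed above by treatment group. Deaths, Kaplan-Meier and the exposure-adjusted tables by system organ class and preferred term are by part, so they are not affected.

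**Share of Part 2 time under the other label.** With Part 2 lasting L weeks, of which the first w are on 0.625, the label is 2.5 if L − w ≥ w and 0.625 otherwise. The minority share is min(w, L − w)/L, with a maximum of 50% at w = L/2. Week 13 is the earliest case used because the escalation criterion (Protocol 5.4.3) needs two consecutive assessments, first scheduled at Weeks 6 and 13 (SAP Table 2-1). Fifty-two weeks is a minimum; 78 is an assumption.

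| w (weeks) | L = 52 | L = 78 |
|---|---|---|
| 13 | 13/52 = 25.0% | 13/78 = 16.7% |
| 19 | 19/52 = 36.5% | 19/78 = 24.4% |
| 26 | 26/52 = 50.0% | 26/78 = 33.3% |

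**Share of all Parts 2 & 3 time when the labels match.** Assume 52 weeks of Part 2 and T years (52 weeks each) of Part 3.

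- Label 2.5/2.5, Part 3 wholly on 2.5: share = w/(52(1 + T)).
- Label 0.625/0.625, just under half of Part 3 on 2.5: upper bound = 0.5T/(1 + T).

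| Case | T = 1 | T = 2 | T = 3 |
|---|---|---|---|
| 2.5/2.5, w = 13 | 12.5% | 8.3% | 6.3% |
| 2.5/2.5, w = 26 | 25.0% | 16.7% | 12.5% |
| 0.625/0.625, bound | 25.0% | 33.3% | 37.5% |

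**Effect on the planned crude-incidence scale.** One misplaced event in one child shifts a column of n children by 1/n: 16.7, 10.0 or 7.7 percentage points for n = 6, 10 or 13 (assumed sizes). This holds only if the child has no event in the same row on the labelled dose, since each child counts once. For n = 10, going from 0 to 1 moves a Clopper-Pearson 95% interval from 0–30.8% to 0.3–44.5%. The method is assumed, as SAP 2.8.2.1 names none.

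**Effect on a rate ratio, illustration only.** Suppose a fraction f of the 0.625 column's person-time is really at 2.5 mg/kg, rates are constant and the true ratio (2.5 to 0.625) is R. Against an unmixed 2.5 column the apparent ratio is R/(1 − f + fR). With R = 2:

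- f = 0.25 × 0.20 = 0.05 (a quarter of children switch, 20% of their time): 2/1.05 = 1.90
- f = 0.50 × 0.40 = 0.20 (half switch, 40% of their time): 2/1.20 = 1.67

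The documents give no rates or switch dates, so R and f are assumptions.

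**The case against.** The strongest reply is that this is a declared convention. The rule is defined openly, a column label classifies a child rather than attributing each event, and a child labelled 0.625/2.5 did receive both doses. The Part 2 objective concerns 52 weeks of dosing, whereas the move to 2.5 mg/kg came later, in Part 3. Escalation inside Part 2 is exceptional, and no count is given. SAP 2.5 promises the display by administered dose, SAP 2.8.1 tabulates duration and frequency by dose, and SAP 2.8.4 shades dose on the individual liver plots. With 25 children, tracing events one by one is feasible. Tables by dose at onset would be sparse, and in upward switchers all 2.5 mg/kg time comes later and at an older age, often after disease progression.

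Some of this stands. The size is unknown, Part 2 switching is only weakly documented, and the added tables need caution. The rest does not remove the point. Part 3 events are pooled into the same Parts 2 & 3 columns that carry Part 2 safety by dose. The promised display states no incidence or denominator, and the exposure table contains no events.

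It could also be argued that the fixed Part 2 dose in SAP 2.1 governs instead. That would enlarge the effect: a child with 52 weeks on 0.625 and then T years on 2.5 would have T/(1 + T) of the time under 0.625, which is 50%, 67% or 75% for T = 1, 2 or 3.

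**Conclusion.** The concern holds. The safety label cannot follow a dose change inside a Part, such changes are allowed and in Part 3 were to be expected, and no specified incidence table restores the dose at onset. SAP 2.1.1 is read as governing because it is the specific safety rule; the other grouping statements are not reconciled with it. Parts of SAP section 4 are redacted and could not be checked.

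The 50% figure is a bound for one child in one Part. The column-level effect cannot be computed and may be small. No test or dose decision depends on it. The change should be made because it affects how safety by dose is described and costs little.

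**What to change.** For Parts 2 & 3, add descriptive TEAE and serious TEAE summaries by *Actual dose* on the day of onset, with time at risk split at each dose change. Keep the existing tables. State in each table shell which grouping it uses. Add one sentence reconciling Protocol 11.1 with SAP 2.1, 2.1.1 and 2.5.

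Footnote the added tables with their limits: sparse cells, carry-over just after a switch, and confounding by age and by the reason for the dose change. For those reasons they supplement the majority-dose tables and do not replace them.

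The cost is programming and SAP wording only. The daily dose variable is already defined and no new data are needed.

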End of study visit will be performed in case of patient discontinuation/early withdrawal. The End of Study visit will have to be performed 30 days after the last treatment.

Part 3 of the study currently does not have a study end defined, taking into account the lethal nature of the SMA Type 1 disease if left untreated. In case the study is discontinued for reasons other than branaplam related patient's safety, patient will continue treatment according to local standard of care, or if not available Novartis will offer available alternative treatment.

Study completion information is mandatory for this visit and must be completed regardless of the patient's completion / discontinuation status.

All other assessments within this visit should be completed, depending on the patient's status and ability to tolerate assessments. For a complete list of assessments, please refer to the Assessment Schedule as presented on Table 7-4.

PK collections

Blood collection for PK will be performed every 6 months. Blood collection will require 2 time points for sample collection, pre dose (C_{through}) and post dose (C4h), therefore the study drug administration should be done onsite, at the day when PK is scheduled. Actual PK sampling times must be documented in the eCRF. Actual date and the time of dosing for the preceding last dose, and the dosing date and time on the day of PK sampling, must be documented in the eCRF.

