Respiratory function																	8
Pulse Oximetry		1						Х				Х				Х	Х
Paradoxical Breathing								X				Х				X	X
Breathing pattern: chest circumference during quiet breathing (sleep)								Х				Х				х	Х
Other assessments			i e	fe .								11			in a		
PK blood collection	X	Х	Х	X	Х												15

Additional instructions on Part 2, Treatment Period 4 assessment schedule:

- ¹ Administration may be done in the patient's home by a qualified clinician or by the assigned and trained caregivers
- ² Questionnaire to be completed ONLY when LMI070 is administered orally
- ³ Detailed neurologic examination must be performed at least monthly (and more often if deemed necessary by the investigator)
- ⁴ If a Grade 2 systolic function AE occurs, echocardiograms will be performed monthly until resolution or until the treatment is withdrawn. Otherwise echocardiograms are to be performed every 3 months
- ⁵ Optional Informed Consent must be obtained before this assessment- up to the discretion of the investigator or parents/guai
- If the patient experience an acute illness episode, these assessment should be performed at a subsequent visit at the discretion of the investigator
- ⁹ if there are no adverse changes detected at both Week 12 and Week 26 visits that can be attributed to branaplam and the branaplam dose is unchanged, then the examination will be performed yearly

¹⁰ For all patients, the end of Study must be completed 30 days after last study drug administration.

Table 7-4 Assessment Schedule – Part 3

7.00000	1													1	1
Part 3	Visit 1	Treat repea	ment a	nd lon ery yea	g term r)	follow	up (aft	ter stud	ly mont	h 12 vis	sit the c	ycle sh	ould be	Unscheduled Visit	End Of Study
Study Month	0	1	2	3	4	5	6	7	8	9	10	11	12	Any time Investigator considers as necessary	30 days after last dose
Days	0	28	56	84	112	140	168	196	224	252	280	308	336	Some or all assessments can be performed as required	30 days after last dose
Visit Window (days)	-14-to 1	+/-7	+/-7	+/-7	+/-7	+/-7	+/-7	+/-7	+/-7	+/-7	+/-7	+/-7	+/-7		+/-7
Visit types: R-Regular, S-Safety	R	s	s	R	s	s	R	s	s	R	s	s	R	R/S	R
Obtain informed consent	Х														
Inclusion /Exclusion criteria	Х														
Current medical conditions	Х														
Drug dispensation/Return	х			х			х			х			x	х	Х
Acceptability and Palatability Questionnaire	х			x			x			x			x	X	x
Safety															
Physical examination	х			х			х			х			х	х	Х
Body weight	х	Х	Х	х	Х	х	х	х	Х	х	Х	Х	х	х	Х
Body length	х			х			х			х			х	х	х

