In this study, **'last contact with the subject'** will be the end of study visit, unless an SAE occurs. However, to ensure subject safety, every SAE must be reported to Novartis:

- occurring until 30 days after the last study visit, regardless of causality
- occurring after the 30 days period, if a causal relationship to study treatment is suspected

'Nominal visits' Nominal visits are defined as all scheduled visits as per the clinical study protocol including the EOS visits. The definition of nominal visit excludes unscheduled visits.

'Safety cutoff' Unless explicitly otherwise stated (e.g. SAEs and deaths), data up to and including the safety cutoff will be included in the analysis and data beyond this time point for a given subject will be excluded from the safety analysis. The safety cutoff is defined as the minimum of

- the study day the patient leaves study Parts 1, 2*, or 3
- the database cutoff date (the Final Database Lock date)
- 30 days after permanent study drug discontinuation.
- day of first dose of alternate treatment for SMA

'Efficacy cutoff' Unless explicitly otherwise stated, data up to and including the efficacy cutoff will be included in the analysis and data beyond this time point for a given subject will be excluded from the efficacy analysis. The efficacy cutoff is defined as the minimum of

- the study day the patient leaves study Parts 1, 2*, or 3
- the database cutoff date (the Final Database Lock date)
- day of first dose of alternate treatment for SMA

The following rules will be applied to assign data to part 3:

- a. For datasets/endpoints that have planned visit numbers populated (e.g. HINE, CHOP-INTEND, etc.), the visit number included in the IFC dataset under 'Consent for

additional follow-up study phase' which is the first visit of Part 3 (as confirmed by Cmed) will be used:

i.e. assessments with visit numbers that are \geq that IFC visit number will be assigned to Part 3.

b. For datasets/endpoints that do not have planned visit numbers populated (e.g. AEs, Feeding status, etc.), the visit date that corresponds to the above IFC visit number will be used:

i.e. assessment dates that are \geq that IFC visit date will be assigned to Part 3. In particular, AEs or concomitant medication with start date time \geq that IFC visit date will be assigned to Part 3.

In general, data collected at a visit during the Part 3 will be analysed together with the part the subject came from (i.e. 'Parts 1 & 3', 'Parts 2 & 3').

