The safety cutoff applies to safety analyses only. The only exception to this are serious adverse events and deaths. Any SAEs occurring after the 30 days period, where a causal relationship to study treatment is suspected, will be reported. All deaths will be reported irrespective of safety cutoff.

In general, treatment emergent AEs are defined as events starting after the first dose of study drug that were absent pre-treatment, or events present prior to the first dose but increased in severity after the first dose. This assumes the same AE with increased severity is properly entered as a separate record in the database with start date being the date when severity increases and that a second AE with same severity won't be entered before the same AE is resolved.

For any other safety analyses based on post-baseline abnormalities compared to baseline (i.e. ECGs, vital signs, etc.), where either of the results is not available, the '**missing**' category will be included to avoid any abnormalities being overlooked.

When showing values over time, for subjects who prematurely discontinued the study, study completion visit assessments will be displayed as if they had occurred at the next scheduled visit.

The eGFR is calculated using the MDRD formula. $eGFR [mL/min/1.73 m^2] = 175 \times (\text{serum Creatinine [umol/L]/88.4}) - 1.154 \times (\text{age [years]}) - 0.203 \times (0.742 \text{ if female}) \times (1.212 \text{ if African American})$ ([Levey et al. 2007](#)).

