- Matrix plot of each of the parameters (ALT, AST, Total Bilirubin and Alkaline Phosphatase) maximum post-baseline/ULN normalized (Parts 1 & 3, and Parts 2 & 3)

All above summaries include only data up to and including safety cut off. If there is any value for a parameter outside of the normal range for a subject, then all data of this parameter for that subject will be listed.

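### In Part 3 a compliant End of Study visit can fall after the SAP's 30-day safety cutoff, on up to 7 of its 15 permitted days, depending on a discontinuation date the SAP does not define

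*SAP*

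**What the plan says.** SAP 2.1.1 sets the safety cutoff at the minimum of four dates: leaving the study part, the database cutoff, "30 days after permanent study drug discontinuation", and the first dose of another SMA treatment. Anything recorded later is left out of safety analysis, under a sentence that contains the words "data up to and including the safety cutoff will be included in the analysis and data beyond this time point for a given subject will". The exemption is narrow: "The only exception to this are serious adverse events and deaths". SAP 2.8 repeats the restriction for safety analyses in general and SAP 2.8.2 for treatment-emergent adverse events. SAP 2.8.4 closes the laboratory summaries with "All above summaries include only data up to and including safety cut off", and SAP 2.8.6 says the same for vital signs.

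For Part 3, Protocol 3.3 says: "The End of Study visit will have to be performed 30 days after the last treatment". In Protocol Table 7-4 the End of Study column reads "30 days after last dose". The row that begins "Visit Window (days) -14-to 1 +/-7" also gives plus or minus 7 days in that column. For Part 2, a note to Table 7-3 says "For all patients, the end of Study must be completed 30 days after last study drug administration", with no tolerance, and the Part 1 schedules are worded in the same way.

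Two other rules in SAP 2.1.1 bear on the point. End of Study visits count as nominal visits, which are the visits mapped into analysis windows. For children who stop early, completion-visit results are to be shown under the next scheduled visit. The SAP does not say on which date permanent discontinuation is taken to occur.

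**The concern.** Day 30 is both the target for the final visit and the last day on which its data count. A visit held a few days late, but within the protocol's own tolerance, can therefore be collected in full and then left out of the safety summaries.

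The Part 3 End of Study visit is a full safety visit. Table 7-4 schedules laboratory tests, ECG, echocardiogram, nerve conduction and an ophthalmologic examination there. Between such visits echocardiograms are 6-monthly, and eye examinations may be yearly when nothing has been found. Losing the visit could leave the last summarised echocardiogram about 6 months old and the last eye examination about 12 months old. Safety is the primary objective of Part 3, and 38 children have been treated in the whole study, so single visits matter.

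The rule also sits badly with the rest of SAP 2.1.1. The efficacy cutoff has no 30-day limb. With discontinuation dated at the last dose and no other limb in force, HINE results from an End of Study visit on day 33 would be kept, while ECG and liver results from the same visit would leave the summaries.

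**Working it through.** The plan gives no figure for the share of visits affected, so there is none to reproduce. The check is a count of days.

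**Inputs**
- Visit target: day 30 after the last dose (Protocol 3.3 and Table 7-4).
- Visit window, Part 3: plus or minus 7 days (Table 7-4).
- Cutoff limb: discontinuation date plus 30 days, with that day itself included (SAP 2.1.1).
- Discontinuation date: not defined. Write it as last dose plus *k* days. As an assumption, *k* is varied from 0 to 7.

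**Formula**
- Permitted days: 30 − 7 = 23 to 30 + 7 = 37, which is 37 − 23 + 1 = 15 days.
- Cutoff day: 30 + *k*.
- Permitted days after the cutoff: 37 − (30 + *k*) = 7 − *k*.
- Share: (7 − *k*)/15.

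**Results**

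| Discontinuation dated at | Cutoff day | Permitted days excluded | Share |
|---|---|---|---|
| Last dose (*k* = 0) | 30 | 7 of 15 | 46.7% |
| Last dose + 2 | 32 | 5 of 15 | 33.3% |
| Last dose + 4 | 34 | 3 of 15 | 20.0% |
| Last dose + 6 | 36 | 1 of 15 | 6.7% |
| Last dose + 7 | 37 | 0 of 15 | 0% |

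**Which row applies.** SAP 2.4.1 points in two directions. The compliance rule counts expected doses up to treatment discontinuation and computes them from the last treatment day, which suggests *k* at or near 0. The exposure formula runs to last dose plus 6, which would give *k* = 6. Dating discontinuation at the first weekly dose not given would give *k* = 7.

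**With the limb extended to day 37.** No permitted day is excluded by this limb. Per child, the extension adds at most 7 days, or 7/30.4375 = 0.23 months on the SAP's month scale. The other three limbs still apply.

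**The case against.** A reader might infer that nearly half of all final safety visits are thrown away. The documents do not support that, for three reasons.
- 7 of 15 is a share of calendar days. It becomes a share of visits only if visits are spread evenly over the window, and no visit timing is given.
- It needs discontinuation to be dated at the last dose. Other readings of the SAP bring it down to 1 of 15 or to none.
- The tolerance is stated only for Part 3. In Parts 1 and 2 the visit is set at day 30, which the cutoff includes.

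A reader might also infer that the results are lost altogether. They are not. All adverse events, ECG data, vital signs and nerve conduction results are to be listed. Echocardiogram and eye data are listed for children with an abnormality, and laboratory records for any parameter with an out-of-range value. All deaths, and later serious events suspected to be related, are reported. Troponin and NTproBNP are collected at the visit, but the visible SAP plans no summary of them and SAP Table 5-4 omits them, so no planned cardiac-enzyme summary can be shown to be affected. Nor is this visit necessarily the only look after stopping: Protocol 7 and 8.1.1 also mention end-of-treatment and follow-up visits, and unscheduled visits are allowed.

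The display rule for completion visits can be read as keeping the data in. However, the SAP names serious events and deaths as the only exception, so the two rules conflict and neither is said to prevail.

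Finally, a fixed 30-day period is a defensible choice. The longest mean half-life reported for Parts 1 and 2 in Protocol 1.1.1 is 59.3 h, so 30 days is 720/59.3, or about 12 half-lives, and a flexible end date makes follow-up length depend on scheduling. That supports a limit near 30 days. It does not support a limit that cuts through the protocol's own visit window.

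**Conclusion.** The mismatch is in the text and should be reconciled. In Part 3, between 0 and 7 of the 15 permitted End of Study days (0% to 47%) fall after the safety cutoff. The upper figure holds if discontinuation is dated at the last dose. How many visits are affected cannot be stated from the documents.

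What can be lost is a compliant visit's contribution to safety summaries, shift tables and non-serious adverse event counts; most listings survive. The result also assumes that no other limb of the cutoff bites first. If the child has already started another SMA treatment, the data are excluded in any case.

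**What to change.** Three linked changes to the SAP:
1. In 2.1.1, define permanent study drug discontinuation as the date of the last non-zero dose.
2. In 2.1.1, set this limb of the safety cutoff to the later of 30 days after that date and the date of an End of Study visit held within its window, so day 37 at most. Keep the other three limbs, including the one for alternate SMA treatment, which still guards against contamination.
3. In 2.4.1, use the same limit in the adverse event time-at-risk formula. Without this, the exposure-adjusted incidences in 2.8.2 would count events on days 31 to 37 with no matching person-time.

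The first change must not be made alone, because it fixes the anchor at the date with the largest loss. The end-date imputation in Table 5-2 already refers to the safety cutoff and would follow.

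No visit, assessment or treatment changes. The cost is up to 7 more off-drug days per child in the safety period, and a follow-up limit that varies between 30 and 37 days.
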